Interim Analysis: Interim database locks will be performed when the 10th patient in Cohort 1, Group 3 exits the study (First Interim Analysis) and when the last patient enrolled in Cohort 1, Group 4 exits the study (Second Interim Analysis). Only data collected up to the last patient exiting the study from Cohort 1, Group 3 will be included in the first data analysis set. All ongoing patients in Cohort 1, Group 4 will remain masked until the second Interim Analysis.

A second interim analysis is planned after the final patient from Cohort 1 exits the study (Cohort 1, Group 4). Outcomes from this analysis will assist in the

confirmation of the study drug concentration and frequency to be used for the Expansion Cohort.

Expansion Cohort:

[figure not shown]
Sample Size Calculation: Estimates for sample size calculations are from the final Cohort 1 interim analysis from Azura Clinical Protocol AZ201801. The mean response of 0.77 and a standard deviation for MGYLS of 2.28 units was observed for control and a mean response of 2.77 units and a standard deviation for MGYLS of 3.35 units was observed for AZR-MD-001 0.5%. A sample size of 45 subjects per group will have 90% power to detect a difference of 2.0 units between the active treatment group and the placebo group using a two-sample t-test at a significance level of 0.05. The standard deviation for Total OSDI was 6.31 units for control and 8.34 units for the high dose. A sample size of 58 subjects per group will have 90% power to detect a difference of 4.52 units between the active treatment group and the control group using a two-sample t-test at a significance level of 0.05. To allow for additional site to site variability the sample size per group will be increased to approximately 75 patients.

Multiplicity Consideration: To address the multiple primary endpoints defined in this study, the primary endpoints have been prioritized into a hierarchical structure. For example, in order to test the primary symptom endpoint of Total OSDI, the primary sign endpoint of MGYLS must be statistically significantly higher in the AZR-MD-001 treatment group compared to the vehicle treatment group using a two-sided significance level of 0.05. The final order of the endpoints will be defined in the Statistical Analysis Plan (SAP) prior to unmasking the study. Using this strategy, the family-wise Type I error rate will be maintained at the 0.05 significance level for the two primary endpoints.

[figure not shown]
Interim Analysis: An interim analysis (Primary Endpoint for the U.S.) is planned after the final enrolled patient completes the month 3 visit. Only an independent biostatistician will be unblinded to the treatment patients actually received and only summary efficacy and safety tables will be provided. Outcomes from this analysis will assist in the confirmation of the study power calculations and potentially as part of a rolling submission to global regulatory agencies.

Figure 1 Study Flow – Multicenter, double-masked, vehicle-controlled, randomized, parallel group study carried out in 2 sequentially overlapping cohorts

a: Cohort 1:

b: Expansion Cohort:

The primary endpoints for the US will serve as an Interim Analyses for the Month 6 primary endpoints. The sample size may be adjusted for power or to address any concerns for alpha inflation.

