1 PROTOCOL SUMMARY

1.1 SYNOPSIS

Study Compound(s): AZR-MD-001 (Selenium Disulfide)

Phase: 2a

Objectives: **Cohort 1:** To evaluate the safety and tolerability of 3 different concentrations of AZR-MD-001 ointment/semi-solid drug (0.1%, 0.5% and 1.0%) applied to the lower lid either twice-weekly or once every evening for up to 3 months compared to its vehicle in patients with meibomian gland dysfunction (MGD) and signs and symptoms of evaporative Dry Eye Disease (DED).

Expansion Cohort: To evaluate the safety, tolerability, and pharmacodynamics of 2 different concentrations of AZR-MD-001 ointment/semi-solid drug (0.5% and 1.0%) applied to the lower lid twice-weekly for up to 6 months compared to its placebo in patients with meibomian gland dysfunction (MGD).

Clinical Hypotheses:

Cohort 1:

At least 1 concentration of AZR-MD-001 ointment/semi-solid drug (i.e., 0.1%, 0.5%, or 1.0%) has an acceptable safety and tolerability profile following twice-weekly, evening ocular administration for the study treatment duration.

At least 1 concentration of AZR-MD-001 ointment/semi-solid drug (i.e. 0.1%, 0.5%, or 1.0%) has an acceptable safety and tolerability profile following once daily, evening ocular administration for the study treatment duration.

At least 1 concentration of AZR-MD-001 ointment/semi-solid drug (i.e., 0.1%, 0.5%, or 1.0%) is more effective than vehicle for treating MGD as measured by the meibum gland secretion score (MGS), the number of Meibomian Glands Yielding Liquid Secretion (MGYLS), or the proportion of patients improving on both a gland score (e.g., MGS or MGYLS) and a patient reported outcome measure (e.g., OSDI).

At least 1 concentration of AZR-MD-001 ointment/semi-solid drug (i.e., 0.1%, 0.5%, or 1.0%) is more effective than vehicle for treating Evaporative DED as measured by either a sign (e.g., TBUT) or symptom (e.g., eye dryness measured by VAS or OSDI).

Clinical Hypotheses: **Expansion Cohort:**

AZR-MD-001 ointment/semi-solid drug (0.5% or 1.0%) has an acceptable safety and tolerability profile following twice-weekly, evening peri-ocular administration for the study treatment duration.

AZR-MD-001 ointment/semi-solid drug (0.5% or 1.0%) is more effective than placebo for treating MGD as measured by the meibomian glands yielding liquid secretion score (MGYLS).

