1.2 SCHEMA

Study Design: *Structure:* Multicenter, double-masked, vehicle-controlled, randomized, parallel group study carried out in 2 sequential cohorts - Cohort 1: sequential rising concentrations of AZR-MD-001 ointment/semi-solid drug (i.e., 0.1%, 0.5%, or 1.0%) and AZR-MD-001 vehicle dosed twice-weekly and/or once daily in the evening; Expansion Cohort: parallel doses of two concentrations of AZR-MD-001 ointment/semi-solid drug (i.e., 0.5% and 1.0%) and AZR-MD-001 placebo dosed twice-weekly in the evening.

Cohort 1:

For Cohort 1, 2 sequential groups of 10 patients each will be followed by 2 sequential groups of 20 patients each. All patients will be diagnosed with MGD and signs and symptoms of Evaporative DED and they will be randomly assigned in a 4:1 ratio to receive either a single concentration of AZR-MD-001 ointment/semi-solid drug (i.e., 0.1% for Group 1, 0.5% for Group 2, 1.0% for Group 3, and a 0.5% for Group 4) or AZR-MD-001 vehicle twice weekly for 1 month. The patients in either the active or vehicle groups will further be assigned in a 1:1 ratio to 1 of 2 treatment regimens at the baseline visit: 1) they will receive treatment twice weekly for their entire 3 month treatment period; or 2) they will receive treatment twice weekly for the first month of their treatment period and will then receive treatment once every evening for months 1 to 3 of their treatment period. At the day 14 visit for the 10th patient in groups 1 and 3 and at month 1.5 for group 2, an unmasked Data Review Committee (DRC) will review all the tolerability and safety data for the patients and recommend a starting dose for the next group of patients (i.e., the DRC can elect not to escalate the dose concentration and can instead repeat a dose that has already been tested). At the month 1 visit the investigator will determine, by patient, if the treatment was well tolerated. If the regimen was well tolerated, the patients will continue their assigned dosing regimen (twice weekly dosing) or escalate to once daily dosing, based on their treatment regimen assigned at the baseline visit. If the investigator does not feel it is safe to escalate dosing and it is safe to continue dosing with the current regimen for a particular patient, that patient will be instructed to continue on their current regimen irrespective of treatment assignment.

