- Average VAS at each visit
- Change from Baseline to day14, month 1.5, month 3, month 4.5 and month 6 in worst VAS
- Worst VAS at each visit
- Change from Baseline to day 14, month 1.5 and month 4.5 in Total OSDI
- Total OSDI, OSDI sub-scales, and individual items from the OSDI across visits
- Proportion of patients with a Total OSDI change from baseline > 4.5 , the known minimally important clinical difference (MICD) for early to moderate disease, at month 3 and month 6
- Proportion of patients with a Total OSDI < 13 at each visit
- Number of expressible glands yielding clear meibum at day14, month 1.5, month 3, month 4.5 and month 6
- Eyelid margin erythema/telangiectasias at day14, month 1.5, month 3, month 4.5 and month 6
- Corneal and conjunctival staining (0 to 5 scale) at each visit

Cohort 1 & Expansion Cohort:

Safety:

- Adverse events
- Vital signs
- Study medication tolerability as measured by the Ocular Comfort Questionnaire (Cohort 1 only)
- Urine pregnancy test
- Best-corrected visual acuity (BCVA; Logarithmic visual acuity chart)
- Biomicroscopy
- Ophthalmoscopy
- Intraocular pressure (IOP)
- Lab analysis of blood and urine (including hematology, chemistry, and urinalysis) (Cohort 1 only)

General Statistical

Methods and Types of Analyses:

The safety population will include all treated patients. For safety variables, patients in the safety population will be analyzed by the treatment actually received. The modified intent-to-treat (mITT) population will be comprised of all patients randomized and, who have values at randomization, and at least 1 post-randomization value for MGS at a regularly scheduled visit (i.e., Day 14 or Month 1 (Cohort 1) or Month 1.5 (Expansion Cohort)). All patients in the mITT population will be analyzed by the treatment received. This population will be used for the primary and the secondary efficacy analyses.

The modified intent-to-treat 2 (mITT2) population will be comprised of patients who are included in the mITT and have the randomization MGS score in the study eye ≥ 6 and ≤ 12 . The mITT2 population will be analyzed by the treatment received.

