9.4.6 PLANNED INTERIM ANALYSES

Two official interim analyses are planned for Cohort 1 of the study. The first interim analysis is planned for after the 10th patient in Cohort 1, Group 3 exits the study. Only data collected up to the last patient exiting the study from Cohort 1, Group 3 will be included in the first interim analysis. All ongoing patients in Cohort 1 will remain masked until the second interim analysis.

A second interim analysis is planned after the final patient from Cohort 1 exits the study (Cohort 1, Group 4). Outcomes from this analysis will assist in the confirmation of the study drug concentration and frequency to be used for the Expansion Cohort.

One interim analyses is planned for the Expansion Cohort of the study. The interim analysis is planned for after the last enrolled patient completes the month 3 visit. Only data collected up to the month 3 visit will be included in the interim analysis. The primary endpoints for the US will serve as an Interim Analyses for the Month 6 primary endpoints. The sample size may be adjusted for power or to address any concerns for alpha inflation.

A final database lock will occur at the completion of the Expansion Cohort and the safety, tolerability, and efficacy data from Cohort 1 and the Expansion Cohort will be analyzed separately and in a combined fashion. At the final analysis, statistical significance will be declared for 2-sided p-values ≤ 0.05 .

Given the exploratory nature of Cohort 1 no adjustments for multiplicity will be applied across the primary or secondary endpoints in this cohort. Multiplicity will be controlled across the primary endpoints in the Expansion Cohort as described in Section 9.4.1.

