4.2. Modified Intent-to-Treat Analysis Set

The Modified Intent-to-Treat (mITT) Set will be comprised of all randomized patients who meet inclusion/exclusion criteria, have MGS values at randomization, have baseline OSDI <34, and received 1 or more applications of randomized study treatment. All patients in the mITT Set will be analyzed by the treatment as randomized. This population will be used for primary efficacy analyses.

4.3. Per-Protocol Analysis Set, Month 3

The Per-Protocol (PP) Set will be comprised of all mITT patients who do not have a Grade 4 or Grade 5 protocol deviation impacting Baseline through Month 3 (as per [Section 7](#)). Deviations which end before the Baseline visit date or begin after the Month 3 visit will not impact inclusion in the PP Set. All patients in the PP Set will be analyzed by the treatment as randomized. The PP Set will be used for primary efficacy analyses.

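### Cohort 1's as-received grouping, with a tolerability-based hold-back at Month 1, can bias daily versus twice-weekly results in favour of daily dosing if treatment received includes dosing frequency

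*Protocol*

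**What the plan says.** Protocol 1.2 (repeated in 4.1) randomizes Cohort 1 patients 4:1 to AZR-MD-001 or vehicle. Within each arm they are to "further be assigned in a 1:1 ratio to 1 of 2 treatment regimens at the baseline visit": twice weekly for three months, or twice weekly for one month and every evening after that. At Month 1 the investigator judges tolerability patient by patient. Where escalation is thought unsafe but continuing is safe, "that patient will be instructed to continue on their current regimen irrespective of treatment assignment".

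The analysis rules are in Protocol 1.2, General Statistical Methods, and again in 9.2. For efficacy: "All patients in the mITT population will be analyzed by the treatment received", and "This population will be used for the primary and the secondary efficacy analyses". For safety, a different sentence applies: "For safety variables, patients in the safety population will be analyzed by the treatment actually received".

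Frequency is one of the questions Cohort 1 is meant to answer. One hypothesis in the Synopsis is that at least one concentration "has an acceptable safety and tolerability profile following once daily, evening ocular administration for the study treatment duration". Protocol 1.2 says each frequency will be evaluated for safety and tolerability in Cohort 1. Of the second interim analysis, Protocol 9.4.6 says: "Outcomes from this analysis will assist in the confirmation of the study drug concentration and frequency to be used for the Expansion Cohort".

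The SAP supplied covers only the Expansion Cohort and refers to a separate Cohort 1 SAP (SAP 1). Its own efficacy rule differs from the protocol's: "All patients in the mITT Set will be analyzed by the treatment as randomized".

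**The concern.** The hold-back is a post-randomization decision based on how the patient has done so far. If patients are then grouped by the frequency they actually used, a patient has to pass the Month 1 tolerability check to be counted as daily. Those who fail it, although randomized to escalate, are added to the twice-weekly group. Patients assigned to escalate who stop before Month 1 would also count as twice weekly, because they never took a daily dose. The daily group is then a selected, more tolerant subset, and the twice-weekly group carries extra intolerant patients.

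At stake is the Cohort 1 statement on how well daily dosing is tolerated, and any efficacy result split by regimen. For efficacy, grouping as received gives up the protection of randomization; the documents do not allow the direction or size of that bias to be worked out. Protocol 9.4.6 still plans a separate Cohort 1 analysis at the final database lock, so the rule has yet to be applied there.

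**Working it through.** **Planned numbers (Protocol 1.2).** Group sizes are 10 + 10 + 20 + 20 = 60, which reproduces the stated total of approximately 60. At 4:1, 60 × 4/5 = 48 active and 12 vehicle. At 1:1 by regimen, 24 active patients are assigned to each regimen: 4 at 0.1%, 12 at 0.5% and 8 at 1.0%.

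**Does treatment received include frequency?**

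- Suggesting yes: being held back changes only frequency, so the hold-back sentence in Protocol 1.2 must count regimen as part of the treatment assignment. The hypotheses in the Synopsis and the frequency evaluation in Protocol 1.2 need results by frequency, and as received is the only grouping rule the protocol gives.
- Suggesting no: the Cohort 1 tests are each AZR-MD-001 group versus vehicle (Protocol 1.2, 9.4.1), the ANCOVA factor is active drug versus vehicle or placebo (9.4.2), and SAP 10 lists dosing regimens separately from treatments.

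The documents leave it open, so what follows is conditional on the first reading.

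**Illustration, true regimen difference set to zero.** The documents give no hold-back or event rates; the values of f, qT and qI below are assumptions.

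- n = 24 active patients assigned to each regimen
- f = proportion intolerant at Month 1, equal in both regimens; all such patients assigned to escalate are held back, so h = n × f
- qT, qI = risk of an event after Month 1 in tolerant and intolerant patients, the same on either frequency

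By assigned regimen, both arms show m = f × qI + (1 − f) × qT.
By regimen received, daily shows qT and twice weekly shows (n × m + h × qI) / (n + h).
The spurious gap simplifies to 2f(qI − qT) / (1 + f).

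Worked case with f = 25%, qT = 15%, qI = 60%: h = 6 and m = 0.25 × 60% + 0.75 × 15% = 26.25%. Daily received is 18 patients at 15%. Twice weekly received is 30 patients with 24 × 0.2625 + 6 × 0.60 = 6.3 + 3.6 = 9.9 expected events, or 33%. The gap is 18 points, against 0 by assigned regimen.

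| f | qT / qI | Both arms, assigned | Daily, received | Twice weekly, received | Spurious gap (points) |
|---|---|---|---|---|---|
| 10% | 10% / 40% | 13.0% | 10% | 15.5% | 5.5 |
| 10% | 15% / 60% | 19.5% | 15% | 23.2% | 8.2 |
| 20% | 10% / 40% | 16.0% | 10% | 20.0% | 10 |
| 20% | 15% / 60% | 24.0% | 15% | 30.0% | 15 |
| 25% | 10% / 40% | 17.5% | 10% | 22.0% | 12 |
| 25% | 15% / 60% | 26.25% | 15% | 33.0% | 18 |
| 0, or qI = qT | any | same in all | same | same | 0 |

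**The case against.** The strongest reply is that treatment means drug and concentration. On that reading a held-back patient stays in the same analysis group and nothing is distorted. The named Cohort 1 comparisons fit this, and no daily versus twice-weekly test is specified. The reply stands as a real possibility. It does not remove the need for a change, because the protocol would then have no grouping rule for the frequency question it asks.

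Second, the Cohort 1 SAP and the Data Review Committee's analysis plan were not available. Either may already group as randomized, as the Expansion SAP does. That stands too.

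Third, safety by treatment actually received is conventional, and grouping by assigned regimen has its own weakness: patients who never took a daily dose count toward the daily arm, which can dilute harms of daily dosing. This is why the as-received safety table should stay, with the assigned-regimen table beside it.

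Fourth, the consequences are bounded. Cohort 1 is described as exploratory (Protocol 9.4.6), its size was set empirically (9.1.1), and only twice weekly was taken into the Expansion Cohort.

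Two stronger inferences are tempting but not supported. One is that daily dosing does look falsely safe. The documents show neither that anyone was held back nor that results are tabulated by frequency received. The other is a much larger gap, obtained by counting Month 1 intolerance itself as the event. That gives 0% for daily against 2f / (1 + f) for twice weekly: 18%, 33% and 46% for f of 10%, 20% and 30%. The zero is built in, since the same event both selects the patients and is counted as the outcome. It also arises while dosing is still identical in the two regimens, so it says nothing about daily dosing.

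**Conclusion.** The point holds conditionally. The protocol contains both the tolerability-based override of a randomized regimen and an as-received rule for efficacy and safety. If that rule extends to frequency, the tolerability comparison is biased toward daily dosing and against twice weekly whenever Month 1 intolerance predicts later events. The size cannot be determined: about 5 to 18 points under the assumed rates for 10% to 25% held back, and zero at the limits shown. For efficacy, grouping as randomized is the better rule on either reading.

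A reader might infer that the bias contaminated the choice of regimen for the Expansion Cohort. The documents do not support that: any such bias runs against twice weekly, the regimen that was selected. The value of the correction is in accurate Cohort 1 reporting.

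**What to change.** In Protocol 1.2 and 9.2, and in the Cohort 1 SAP if it repeats the rule:

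1. Analyse Cohort 1 mITT efficacy by randomized concentration and regimen, in line with the as-randomized rule in SAP 4.2.
2. Keep the as-received safety table. Where it is split by frequency, label the daily column as a selected group.
3. Add a safety table that pools over regimen before Month 1, when dosing is the same, and groups by assigned regimen after Month 1.
4. Report, by arm, the number not escalated and the reasons.

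The cost is wording, one grouping variable and one added table. No new assessments are needed, since regimen is assigned at baseline, although the protocol does not say in which system that assignment is stored. There is a small downside to state with the results: the assigned-regimen figures estimate the policy of escalating if tolerated. They do not show the safety of daily dosing in patients who never received it.

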1.3 SCHEDULE OF ACTIVITIES (SOA) COHORT 1 AND EXPANSION COHORT

Table 1 Schedule of Visits and Procedures

Study Period	Qualification		Double-Masked Period						
	Screening ^a (Day -14)	Baseline Day 0 Randomization	Day 14	Month 1 (Coh.1 only)	Month 1.5	Month 3 (Exit Coh.1)	Month 4.5 (Expan.)	Month 6 (Exit Expan.)	
NOTE: The recommended order for the procedures to be followed appears in the Procedure Manual									
Visit Window	± 2 Days	N/A	± 2 Days	± 7 Days	± 7 Days	± 2 Days	± 7 Days	± 2 Days	
Informed consent/authorization	X								
Contact IVRS/IWRS for patient number assignment (screening number)	X								
Demographics (including height and weight)	X								
Inclusion/exclusion criteria	X	X							
Medical and ophthalmic history	X	X							
Medication history	X								
Washout medications	X								
Vital signs (pulse rate, blood pressure)	X	X		X		X		X	
Pregnancy test (urine) for female patients ^b	X					X		X	
Patient Ocular Symptoms (VAS)	X	X	X	X	X	X	X	X	
OSDI	X	X	X	X	X	X	X	X	
SPEED	X	X	X	X	X	X	X	X	
Best-corrected visual acuity (BCVA)	X ^c	X	X	X	X	X	X	X	
Slit-lamp biomicroscopy (includes eyelid margin erythema/telangiectasias and do not touch the	X	X	X	X	X	X	X	X	
Oculus Keratograph 5® procedures: interferometry, redness test, and/or lower lid meibography photograph (selected sites) ^d	X	X	X	X	X	X			
LipiView® interferometer (selected sites) ^d	X	X	X	X	X	X			
Tear Break Up Time (TBUT) ^g	X	X	X	X	X	X	X	X	
Sodium fluorescein corneal staining, Oxford scale	X	X	X	X	X	X	X	X	
Lissamine green conjunctival staining, Oxford scale	X	X	X	X	X	X	X	X	

Study Period	Qualification		Double-Masked Period						
	Screening ^a (Day -14)	Baseline Day 0 Randomization	Day 14	Month 1 (Coh.1 only)	Month 1.5	Month 3 (Exit Coh.1)	Month 4.5 (Expan.)	Month 6 (Exit Expan.)	
NOTE: The recommended order for the procedures to be followed appears in the Procedure Manual									
Visit Window	± 2 Days	N/A	± 2 Days	± 7 Days	± 7 Days	± 2 Days	± 7 Days	± 2 Days	
Meibomian gland evaluation (MGE) ^g	X	X	X	X	X	X	X	X	
Schirmer without anesthesia	X	X		X		X		X	
Tear Collection for biomarker analysis (selected sites) ^d		X		X		X			
Intraocular pressure (IOP)	X					X		X	
Ophthalmoscopy exam ^e	X					X		X	
Meibography	X					X		X	
Lab – Blood safety (chemistry , hematology) and urinalysis (Cohort 1 Only)	X					X			
Study medication Tolerability/Comfort Questionnaire (Cohort 1 only) ^f		X	X	X	X	X			
Adverse events/medications/procedures	X	X	X	X	X	X	X	X	
Discontinue concomitant medication(s) impacting inclusion/exclusion	X								
Contact IVRS/IWRS for patient randomization number		X							
Medication dispensing/return	X (Cohort 1)	X		X	X	X	X	X	
Physician Observation of Drug Application	X (Cohort 1)	X							

BCVA = Best Corrected Visual Acuity; Coh. = Cohort; Expan. = Expansion; OSDI = Ocular Surface Disease Index; SPEED = Standard Patient Evaluation of Eye Dryness; TBUT = tear break up time; VAS = Visual Analogue Scale; PM = Evening, Month = 28 days

a Screening diagnostic procedures are not required to be performed on the same day, and can be performed across multiple days from days -14 to -2. At screening, patients will be asked to report use of artificial tears and all other treatments for MGD and/or DED. Patients should wash out from all medication listed in the inclusion/exclusion criteria. The screening period includes a 2-week, run-in with AZR-MD-001 placebo for Cohort 1. Patients who are re-enrolled following an initial screen failure will receive a new screening number upon re-screen (i.e., sites should not reuse the old number).

b For females of childbearing potential.

c Manifest refraction performed at screening will be used at each visit to obtain BCVA.

d Performed as a sub-study by selected sites and patients and approved by study sponsor.

e Ophthalmoscopy examination will be dilated at screening and undilated for study exit unless dilation is necessary

f Instill dose of medication after completing safety/efficacy measures and ~5 minutes before medication tolerability assessment (see Procedure Manual for more detail).

g TBUT and MGE should be performed by the same individual for a given patient. For the Expansion Cohort, the individual performing the measurement will not be involved in drug dispensing or accountability and should remain masked to the treatment received by the patient.

